**2.0 Background**

Chronic cough, defined as a cough lasting greater than or equal to 8 weeks, is a common problem with a lifetime prevalence estimated at 7 to 12% in the adult population. These symptoms are often quite frustrating and functionally limiting for these individuals, leading to substantial morbidity. In fact, multiple studies have demonstrated a significant decrease in quality of life, particularly within psychosocial domains, due to chronic cough. Cough severity varies across patients and is often perceived in terms of the frequency of coughing fits or urges, intensity, and disruptions.

A wide differential diagnosis for chronic cough exists, creating substantial diagnostic and treatment challenges. Chronic cough may be secondary to gastrointestinal reflux, pulmonary disease such as asthma or COPD, smoking, upper airway cough syndrome, and/or medication use (i.e. angiotensin converting enzyme or ACE inhibitors). A significant subset of patients, however, are found to have cough related to a sensory neuropathy, also known as a “neurogenic cough.” In these individuals, there is hypersensitivity of the internal branch of the superior laryngeal nerve, likely a result of post-viral infection, that leads to a decreased threshold for the stimulation of afferent cough receptors. This

diagnosis is often one of exclusion, after the other possible etiologies of cough have been thoroughly evaluated.

Several treatments have been explored for neurogenic cough, including the use of neuromodulating medications (i.e. amitriptyline, gabapentin, pregabalin, baclofen, and tramadol). Ryan et al. found that about 67% of patients taking amitriptyline for chronic cough had greater than 50% improvement in symptoms; however, 64% of patients discontinued use of the medication at follow up. Of these patients, 48% discontinued amitriptyline due to its side effects, which include sedation, dry mouth, anxiety, insomnia, weight gain, and dizziness. Similarly, gabapentin and pregabalin have shown some efficacy in the treatment of neurogenic cough, but they are not effective in all patients and there are concerns for systemic medication side effects. Dion et al. have proposed further evaluation of tramadol for neurogenic cough, however, opioid dependence is a significant concern. In addition to neuromodulating medications, suppression (cognitive behavioral) therapy can be a useful adjuvant but is more effective when combined with medical therapy. Lastly, botulinum A injections and injection augmentation have been suggested for chronic cough, but have been found to have limited use in clinical practice.

Superior laryngeal nerve (SLN) blocks, which involve a percutaneous injection of lidocaine and steroid, have been widely described in the Anesthesiology literature as a safe and effective anesthetic during awake fiberoptic intubation. The literature on superior laryngeal nerve blocks for the treatment of chronic cough is limited, but there are two published retrospective studies supporting the efficacy of in-office SLN injections Simpson et al. reported a series of 18 patients who underwent an average of 2.4 SLN blocks with a statistically significant decrease in cough severity index scores from 26.8 to 14.6 following treatment. No significant adverse outcomes were reported. Dhillon similarly showed a statistically significant decrease in post-treatment cough severity index scores following SLN injections in a cohort of 10 patients without any adverse effects.

Recently, we retrospectively reviewed our experience at the Medical University of South Carolina with in-office SLN blocks for the treatment of chronic neurogenic cough and our unpublished data are consistent with the work of Simpson, et al. and Dhillon. We found that within a cohort of 23 patients (4 males, 19 females, average age 63.6 years), 17 (74%) reported improvement with the injections, 2 (9%) reported initial improvement followed by return to baseline, and 4 (17%) did not have any improvement. The average number of SLN blocks performed per patient was 3.8. Of the 23 patients, 13 had recorded pre- and post-treatment Hull Cough Sensitivity Questionnaire scores and changes in scores were significantly improved from an average of 38 to 23 ( $p = 0.005$ ). All patients reported their symptom severity on a scale of 0-10 and there was a significant negative correlation between the number of injections and symptom severity scores with the largest difference following the initial injection (Figure 1). There were no major adverse events, however 4 patients (17%) reported self-limited post-injection globus sensation.

Although the current data support the efficacy and safety of SLN blocks for chronic neurogenic cough, there are no prospective investigations. Questions remain regarding safety and efficacy, particularly the potential for placebo effect, as well as proper medication dosing and timing. Our hypothesis is that superior laryngeal nerve blocks will provide significant improvement in cough severity compared to placebo. By better understanding the efficacy of superior laryngeal nerve blocks in the treatment of chronic cough, the care of patients presenting with this common symptom will be optimized.

### 3.0 Intervention to be studied (if applicable)

As mentioned above, superior laryngeal nerve (SLN) blocks, which involve a percutaneous injection of lidocaine and steroid, have been widely described in the Anesthesiology literature as a safe and effective anesthetic during awake fiberoptic intubation. The literature on superior laryngeal nerve blocks for the treatment of chronic cough is limited, but there are two published retrospective studies supporting the efficacy of in-office SLN injections Simpson et al. reported a series of 18 patients who underwent an average of 2.4 SLN blocks with a statistically significant decrease in cough severity index scores from 26.8 to 14.6 following treatment. No significant adverse outcomes were reported. Dhillon similarly

showed a statistically significant decrease in post-treatment cough severity index scores following SLN injections in a cohort of 10 patients without any adverse effects.

Triamcinolone and lidocaine are both FDA approved injectable medications that have been used in peripheral nerve blocks as mentioned above. The proposed dosing of 2 mL of a 1:1 triamcinolone 40mg: 1% lidocaine with 1:200,000 epinephrine for the superior laryngeal nerve blocks in this study is due to standard practice at MUSC. Similar dosing has been used in the studies mentioned above by Simpson et al. and Dhillon. Saline will be injected as the placebo substance, which has no active ingredient.

#### 4.0 Study Endpoints (if applicable)

Primary study endpoints include improvement in cough, measured by dichotomous yes/no response to improvement, the Leicester Cough Questionnaire (LCQ), and a visual analogue scale for symptom severity. Due to its validation, the LCQ will be the primary outcome measure. Secondary study endpoints include the complication and side effect rate from the injections.

#### 5.0 Inclusion and Exclusion Criteria/ Study Population

A chart review of all participants will be conducted at the initial visit for basic demographic information and co-morbidities. Inclusion criteria includes a history that is consistent with neurogenic cough (i.e. preceding viral illness, cough triggered by normal laryngeal functions such as voicing or laughing, environmental triggers such as perfume or noxious odors, etc.), exclusion of other well-known etiologies of cough and age  $\geq 18$  years. As part of the standard of care at our institution, patients are not treated for neurogenic cough until other etiologies of cough are excluded. Therefore, no funding for this study will be used in the evaluation of gastrointestinal reflux disease (GERD), pulmonary disease, or upper airway cough syndrome, as this is done routinely prior to diagnosis of neurogenic cough. All of our patients prior to enrollment in this study will have normal pulmonary function testing performed since their cough started, and a chest x-ray within the past six months. If a patient has known GERD or a history consistent with laryngopharyngeal reflux with a Reflux Symptom Index (RSI)  $> 13$  or Reflux Finding Score (RFS)  $> 11$ , then the patient will undergo evaluation for GERD including pH testing, EGD, high resolution manometry and/or esophagram. All of this standard of care testing for the evaluation of chronic cough will be done prior to patient enrollment and consent. Exclusion criteria will include patients on ACE inhibitors or Angiotensin II receptor blockers (ARBs), patients with uncontrolled obstructive sleep apnea, current smokers, and current neuromodulating medication use for chronic cough. If a patient presents on a neuromodulating medication, but is weaned off prior to the start of superior laryngeal nerve blocks, they may be included. This scenario may be encountered for those patients in whom a neuromodulating medication was not effective. Former smoking history will be permissible in the absence of pulmonary disease. A list of the inclusion and exclusion criteria are summarized in Table 1, shown below.

**Table 1. Inclusion and Exclusion Criteria for Study Enrollment**

Inclusion Criteria	Exclusion Criteria
History consistent with neurogenic cough Exclusion of other etiologies (see exclusion criteria) Age $\geq 18$	Current neuromodulating medication use Untreated other etiologies of cough Current smoker Current ACE/ARB use Abnormal PFTs obtained after cough started Uncontrolled OSA Abnormal CXR within 6 months RSI $> 13$ or RFS $> 11$ AND Workup positive for GERD (esophagram, 24-hour pH probe, manometry, EGD)

Children will be excluded in this study as they are a vulnerable population and neurogenic cough typically affects older adults.

## **6.0 Number of Subjects**

We will recruit 50 patients. Our institution has several otolaryngologists who routinely treat chronic cough and, within the past year, a single provider performed superior laryngeal nerve blocks on 29 patients, with the majority of the injections occurring within the last 2-3 months. Therefore, we are confident in our ability to recruit 50 patients within 1 year. Assuming a dichotomous outcome of >50% improvement or not, a 70% treatment effect, a 25% possible incidence of improvement in placebo, and an 80% confidence level, we would need 18 patients in each group (total N=36) to power our study.

## **7.0 Setting**

Patients will be recruited and injections will be completed in the ambulatory clinic setting.

## **8.0 Recruitment Methods**

Patients will be seen in ambulatory clinics as part of a standard workup for chronic cough. The research team will also distribute recruitment flyers in common areas of the MUSC campus, particularly in Otolaryngology, Pulmonology and Gastroenterology clinics. Patients will be screened at the initial visit if they meet inclusion criteria or at further visits after additional workup for other sources of cough is completed, patients will be offered participation in the study. The PI and co-investigator will be in the ambulatory clinics to offer participation in the study. Primarily, the principal investigator will discuss risks and benefits of study participation with the eligible subjects using the informed consent form. There will be no additional advertisements; subjects will be recruited within the standard clinical practice of the clinic.

[figure not shown]
## **9.0 Consent Process**

The principal investigator and qualified research staff will be responsible for obtaining informed consent. These qualified team members will sit with patients and run through the informed consent document that describes the purpose of the study and benefits and risks in non-scientific language. This will take place in the clinic. Consent will only be obtained from the participant. There will be no waiting period available between informing the prospective subject and obtaining the consent, unless the patient requests more time to review the document prior to signing the consent form. Consent will not be completed until exclusion and inclusion criteria met.

## **10.0 Study Design / Methods**

Figure 2 depicts the flow diagram of the study design. Once patients have met inclusion and exclusion criteria (including undergoing all diagnostic testing for other potential causes of chronic cough) and have agreed to study participation, informed consent will be obtained and they will be randomized into two groups: treatment and placebo. This will be achieved using randomly-assorted, secured envelopes containing a card indicating whether the patient will be in the treatment or placebo group. This will be unveiled immediately to the provider administering the first injection, but remain unknown to the subject. There will be 25 "Treatment" and 25 "Placebo" cards within the 50, individually-secured envelopes. On initial visit, prior to the injection, patients will first undergo nasal laryngoscopy as part of standard of care. If there is any vocal fold weakness seen on scope examination or if there is a unilateral trigger point identified, then the first injection will start on the side of the suspected neuropathy. If there is no evidence of neuropathy on examination, we will start with a left-sided injection. Injections will be standardized to 2 mL of a 1:1 triamcinolone 40mg: 1% lidocaine with 1:200,000 epinephrine. Injection syringe will be brought into room by the physician in an opaque box and placed behind patient so they cannot view the syringe prior to injection. During the injection, a paper "shield" will be held under the patient's chin by an assistant and they will be asked to close their eyes so that they are not able to view the syringe during injection. This is necessary as steroid possesses a white color as compared to clear saline. The practitioner is not blinded so that proper drawing back on the syringe is not compromised to avoid intravascular or airway injection.

[figure not shown]

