## 15.0 Risks to Subjects

While no major adverse effects following SLN blocks for chronic cough have been reported in the current literature or found in our own experience, potential adverse events could include bruising, bleeding, laryngospasm, dysphagia and/or aspiration, swelling or fluctuance, dysphonia, or infection. Minor discomfort and self-limited globus sensation are not unexpected but typically mild. There is a theoretical potentially severe adverse event of intra-arterial injection resulting in blindness or stroke. The physician will always draw back on the syringe prior to injection to ensure that the needle is not intravascular and will perform a slow injection to prevent retrograde flow into the external carotid system to prevent this theoretical event. The study will be monitored by our Institutional Review Board and will be terminated early if any serious adverse reactions were to occur.

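### As Section 10.0 is ordered, the injector learns the arm before the laryngoscopy that sets the first side and before any last judgement on suitability for injection

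*Combined protocol and SAP*

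**What the plan says.** Section 10.0 starts from patients who meet the criteria and agree to take part: "informed consent will be obtained and they will be randomized into two groups: treatment and placebo". Allocation is by a card in a secured envelope, with 25 cards per arm. Of the card it says: "This will be unveiled immediately to the provider administering the first injection, but remain unknown to the subject".

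The laryngoscopy comes next in the text: "On initial visit, prior to the injection, patients will first undergo nasal laryngoscopy as part of standard of care". Its result sets the first side. If a vocal fold is weak or there is a one-sided trigger point, "then the first injection will start on the side of the suspected neuropathy". Failing that, the default applies: "If there is no evidence of neuropathy on examination, we will start with a left-sided injection".

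One reason is given for leaving the injector unblinded: "The practitioner is not blinded so that proper drawing back on the syringe is not compromised".

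The inclusion column of Table 1 (Section 5.0) reads "History consistent with neurogenic cough Exclusion of other etiologies (see exclusion criteria) Age", followed by the age limit. The exclusion column covers other causes of cough, smoking, sleep apnoea and certain current medicines. No entry records a judgement that the patient is suitable for the study injections. Section 15.0 separately says that "potential adverse events could include bruising, bleeding, laryngospasm, dysphagia and/or aspiration, swelling or fluctuance, dysphonia, or infection".

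**The concern.** Allocation should stay hidden until every decision that could depend on it has been made and written down. Two decisions appear to be left open here.

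- **The first side.** The rule is fixed, but its inputs are judged. Whether a vocal fold is weak, or a trigger point is present on one side, is read from an examination by a clinician.
- **Whether to go ahead.** Table 1 does not ask whether the patient is suitable for the injections, so doubt on that score may first arise at the visit. If the injector already holds the card, a worry about a study drug has more weight when the syringe contains that drug than when it contains saline.

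A randomised patient who is then not injected, or is dropped, for a reason linked to the arm weakens the comparability that randomisation provides. The sections on design and data management do not say how such a patient would be analysed.

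**Working it through.** **1. Order of events**

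| Step | Source | Position |
|---|---|---|
| Listed criteria met | Sections 9.0 and 10.0 | before consent is completed |
| Consent, then randomisation | Section 10.0 | after the criteria are met |
| Card shown to the injector | Section 10.0 | at once |
| Laryngoscopy | Section 10.0 | initial visit, before the injection; order relative to the card not stated |
| First side fixed | Section 10.0 | from the laryngoscopy result |
| Injection | Section 10.0 | last |

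Read in sequence, the card comes before the scope. That is an inference from the order of the text. Section 9.0 allows consent with no waiting period, so all these steps can fall within one visit, where their order matters.

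**2. Does the reason for unblinding require early disclosure?** The reason concerns drawing back on the syringe, which happens at the injection. Nothing in it requires the arm to be known during the laryngoscopy.

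**3. The plan's own figure.** Section 6.0 gives 18 per group for 70% v 25%. I read its 80% as power and assume a two-sided 5% level, which is not stated. With the arcsine formula:

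- h = 2·arcsin(√0.70) − 2·arcsin(√0.25) = 0.935
- n = 2(1.96 + 0.8416)²/h² = 17.95, so 18 per group

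The pooled normal formula gives 19. The figure is reproduced, and it does not depend on this point.

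**4. Power if active patients are lost.** Normal approximation, two-sided 5%, 70% v 25%, with p̄ the pooled rate:

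z = [0.45 − 1.96·√(p̄(1−p̄)(1/n₁+1/n₂))] / √(0.70·0.30/n₁ + 0.25·0.75/n₂)

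- 25 v 25: z = 1.37, power 91.5%
- 22 v 25: z = 1.26, power 89.6%
- 20 v 25: power 88.0%

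**5. Possible bias.** Let k of 25 active patients be dropped after randomisation. The number k and its link to response are assumptions; the documents give neither. If all k are non-responders, the observed rate is 25p/(25 − k):

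| k | share of arm | shift if p = 70% | shift if p = 25% (no effect) |
|---|---|---|---|
| 1 | 4% | +2.9 points | +1.0 |
| 2 | 8% | +6.1 | +2.2 |
| 3 | 12% | +9.5 | +3.4 |
| 5 | 20% | +17.5 | +6.3 |

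If the losses are unrelated to response, the expected shift is zero. If all are responders, the rate is (25p − k)/(25 − k). For k = 3 that is 14.5/22 = 65.9% (−4.1 points) when p = 70%, and 3.25/22 = 14.8% (−10.2 points) when p = 25%. The table therefore shows one extreme and is not a forecast. It uses the yes/no response of Section 6.0, not the Leicester Cough Questionnaire, which is the primary measure.

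**The case against.** The case on the other side has real force.

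- **The sequence is not stated.** The wording on the laryngoscopy allows the scope to come first, and the flow diagram (Figure 2) is not available to settle it. This stands: the point is that the text does not secure the order, not that the wrong order is certain.
- **A reader might infer that late exclusions can fall only on the treatment arm.** The documents do not support that. The only stated removal from analysis is follow-up outside 1 to 4 weeks, and it applies to both arms. Findings at laryngoscopy, and concerns about the needle procedure itself, can arise in either arm. The lidocaine skin cream in Section 10.0 is not restricted by arm, so a lidocaine concern is not confined to one arm either. Placebo patients may later take two active injections, so suitability matters for them too. What remains is that a concern about a constituent of the active injection alone would more naturally be acted on in the active arm.
- **A reader might infer that the injector chooses the side freely.** The side follows a rule with a left default, and only the reading of the scope is open. Section 3.0 describes saline as having no active ingredient, and the primary measure is completed by patients who do not know their arm. The route from side to outcome is therefore narrow, and neither its direction nor its size can be given.
- **A reader might infer that the criteria admit patients who should not receive the drugs.** The documents list no contraindications, so this cannot be established from them. Section 5.0 provides for a chart review of co-morbidities and Section 8.0 for a discussion of risks. Either may bring a problem to light before randomisation, though neither is a written suitability check.

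None of this supplies a reason to disclose the arm before the examination.

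**Conclusion.** The point holds in a limited form. Section 10.0 calls for immediate disclosure to the injector and does not require the laryngoscopy, the suitability judgement or the intended side to be recorded first. As ordered, the text leaves those judgements open to knowledge of the arm, and the reason given for unblinding does not need this.

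The size is unknown. Each loss is 4% of an arm. Three one-sided losses would cost about 2 points of power (91.5% to 89.6%). If all three were non-responders, a true 70% response would appear as 79.5%; if the losses were unrelated to response, the expected bias would be nil. The conclusion rests on reading the order of the text as the order of events. If the scope is already done first in practice, a sentence saying so would settle that part, provided that suitability and side are also recorded before disclosure.

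**What to change.** In Section 10.0, replace immediate disclosure with a stated sequence: the envelope is opened only after the laryngoscopy is done and after three items are recorded, namely confirmed eligibility, the investigator's judgement that the patient is suitable for either study injection, and the intended side of the first injection. The injector then learns the arm in time to prepare and give the injection, so the stated reason for unblinding is still met. The clinical content of suitability is for the investigator; no specific exclusion is proposed here.

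The cost is a reordering of steps within the same visit and a short record, with no added procedure. The downside is that a few consented patients may be screened out before randomisation. Their envelopes stay unopened, so the 25:25 set of cards is not disturbed. The change does not reach the second side, which is decided at follow-up when the injector already knows the arm.

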### **Figure 2. Flow Diagram of Study Design**

Injection will be completed near the lateral thyrohyoid membrane by a single experienced laryngologist per previously published methodology utilizing bony, soft tissue and cartilaginous landmarks. An illustration of the anatomic target for the injection can be seen in Figure 3. To minimize patient discomfort, lidocaine cream will be applied to the skin prior to injections.

Following injection, patients will be instructed to follow up in a 2- to 3-week time frame; however, we will include all patients in analysis if they follow up within 1-4 weeks. Any follow up outside of that window will lead to removal of the patient's data from the analysis. At follow up, if the patient's cough has improved by greater than or equal to 50% compared to baseline, we will repeat the injection on the same side. If less than 50%, we will move to the other side to perform the injection. Patients will undergo a total of two injections before data collection is complete for analysis. If patients were to experience full resolution of cough (i.e. report 0/10 for cough severity) after the first injection alone, then at that point, their condition would be considered cured and their enrollment in the study will finish. The reason for this is to avoid unnecessary and unindicated injections in patients with resolution of cough.

2 weeks after the second injection, participants will be unblinded. If in the placebo group, they will have the opportunity to complete 2 additional treatment injections (unblinded) under the study protocol. Data will be collected and stored in the same fashion as prior to unblinding.

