**Figure 3. Anatomic Target of Superior Laryngeal Nerve Blocks.**

During the procedure, the thyroid cartilage, hyoid, and thyrohyoid membrane are palpated as key anatomic landmarks. The target of the injection, the superior laryngeal nerve, pierces the thyrohyoid membrane superior to the superior laryngeal artery. The plunger is drawn back prior to injection to ensure needle tip is not intravascular. Illustration by author.

Patients will be provided a log to track their progress throughout treatment. This will include a visual analogue scale to be completed daily after each injection to document cough severity, as well as opportunities to document any adverse effects or general comments. An example of this log can be seen in Figure 4. At each follow up visit, patients will provide a dichotomous answer (Yes or No) if they experienced improvement in cough and will disclose how long the improvement lasted. They will also fill out the Leicester Cough Questionnaire (LCQ), a validated 19-question quality of life survey for chronic cough. The LCQ will be the study's primary outcome measure. Please see Appendix 1 for a copy of the Leicester Cough Questionnaire. After the last injection, patients will return to the clinic in three months or opt to be contacted via telephone to assess if symptoms have returned.

Date of last injection: _____
 
WEEK 1  Please mark on the line below with a "X" how severe you believe your cough is. The far left indicates no cough at all, and the far right is indicative of the most severe cough.
 
Day 1 no cough ..... severe cough
 
Day 2 no cough ..... severe cough
 
Day 3 no cough ..... severe cough
 
Day 4 no cough ..... severe cough
 
Day 5 no cough ..... severe cough
 
Day 6 no cough ..... severe cough
 
Day 7 no cough ..... severe cough
	

Date of last injection: _____
 
WEEK 2  Please mark on the line below with a "X" how severe you believe your cough is. The far left indicates no cough at all, and the far right is indicative of the most severe cough.
 
Day 1 no cough ..... severe cough
 
Day 2 no cough ..... severe cough
 
Day 3 no cough ..... severe cough
 
Day 4 no cough ..... severe cough
 
Day 5 no cough ..... severe cough
 
Day 6 no cough ..... severe cough
 
Day 7 no cough ..... severe cough
	

Any side effects?
	
Any side effects?

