## 12.0 Data Management

Descriptional analysis of all demographic data, including sex and age, will be completed. Dichotomous data will be summarized as percentages per group per injection and compared via chi-squared analysis. Changes in Leicester Cough Questionnaire scores, both global and specific domains (physical, psychological and social), will be analyzed via a linear regression model. An independent t-test will then be used to compare both study arms. Regression analysis will also be performed on the data collected from the patient log, specifically the daily visual analogue scale. A ruler will be used to the identify the exact percentage along the scale that represents the patient's cough severity. A comprehensive compilation of side effects reported by the treatment group will be reported as a proportion of the total number of patients in the treatment study arm (n = 25) and compared to the placebo group (n=25). The data collected from the placebo group pre-unblinding will be directly compared to the results achieved from treatment injections offered following unblinding.

Data will not leave MUSC. Patient identifiers (MRN) will be kept coded on a separate, password-protected file stored on a secure drive.

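### Randomised patients who return outside 1-4 weeks are removed from the analysis and no as-randomised LCQ comparison is planned, so the primary result is open to bias if removal relates to outcome differently by arm

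*Combined protocol and SAP*

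**What the plan says.** Section 10.0 (Study Design / Methods) randomises patients after consent and before the first injection, using 25 envelopes per arm. The text under the Figure 2 heading asks them to return 2 to 3 weeks after an injection and accepts 1 to 4 weeks for analysis. It then says: "Any follow up outside of that window will lead to removal of the patient's data from the analysis". It does not say whether one out-of-window visit costs that visit's data or all of the patient's data. Nor does it deal with patients who never return.

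Section 4.0 settles the primary outcome: "Due to its validation, the LCQ will be the primary outcome measure". The text under the Figure 3 heading has the LCQ completed at each follow-up visit, which is the visit the window governs. For the LCQ, section 12.0 (Data Management) plans a linear regression of changes, and then: "An independent t-test will then be used to compare both study arms". It names no analysis set, missing-data method or sensitivity analysis. Full-arm denominators (n = 25 and n = 25) appear only for side effects.

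**The concern.** Randomisation makes the arms comparable at the moment of assignment. A rule that later drops patients by when they came back replaces that comparison with one between selected groups. A patient who attends in week 5 and completes the LCQ has supplied the primary outcome, yet it is not used.

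This does harm only if removal is tied to outcome differently in the two arms. Such routes are possible here. The injecting provider knows the allocation. After the second injection, "2 weeks after the second injection, participants will be unblinded", and placebo patients are then offered open-label injections, while follow-up is accepted to 4 weeks. The documents do not say that either affects when patients return.

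At stake is the prespecified status of the answer. Late LCQs would be left out of the analysis rather than destroyed, so an as-randomised result could still be produced, but it would be post hoc and would contradict the written rule.

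**Working it through.** **1. The plan's own figure.** Section 6.0 assumes 70% v 25% on a dichotomous outcome and concludes: "we would need 18 patients in each group (total N=36) to power our study". I read its 80% confidence level as 80% power and assume a two-sided 5% test, since no alpha is given.

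- Pooled normal formula: n = [(1.960 × √(2 × 0.475 × 0.525) + 0.842 × √(0.70 × 0.30 + 0.25 × 0.75)) / 0.45]² = [(1.384 + 0.531) / 0.45]² = 18.1, so 19 per group.
- The arcsine formula gives 18. The stated figure reproduces.

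**2. Power if removal is unrelated to outcome.** Power = Φ[(0.45√n − 1.384) / 0.630].

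- 25 per arm: 91.5%
- 20 per arm (20% removed): 84%
- 18 per arm (28% removed): 80%

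These figures are for the dichotomous outcome. The documents give no LCQ standard deviation or target difference, so LCQ power cannot be computed.

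**3. Bias under assumed removal.** The documents give no out-of-window rate and no link between lateness and outcome, so every rate here is an assumption. Take normal outcomes with SD 1, no true effect and 25 per arm. Let b and a be the removal rates below and above the mean, and f = (a + b)/2 the overall rate. Half the mean of a half-normal variable is 0.399, so the mean of those kept is

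m = 0.399 × (b − a) / (1 − f).

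The shift is the difference in m between arms. Retained means used below:

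- 2:1 selection (b = 2a): f = 10% gives 0.399 × 0.0667/0.9 = 0.0296; f = 20% gives 0.399 × 0.1333/0.8 = 0.0665; f = 30% gives 0.399 × 0.2/0.7 = 0.1140.
- Only below-mean removed (a = 0): f = 10% gives 0.399 × 0.2/0.9 = 0.0887; f = 20% gives 0.399 × 0.4/0.8 = 0.1995; f = 30% gives 0.399 × 0.6/0.7 = 0.3420.

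Type I error comes from 200,000 simulated trials with a pooled two-sided t-test at 5%. The simulated shifts agree with the formula to within 0.001 SD.

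| Removed, arm v arm | Selection | Shift (SD) | Type I error |
|---|---|---|---|
| 10% v 10% | 2:1, same in both arms | 0.00 | 5.0% |
| 19% v 19% | 2:1, same in both arms | 0.00 | 5.0% |
| 20% v 10% | 2:1 below-mean | 0.0665 − 0.0296 = 0.037 | 5.2% |
| 30% v 10% | 2:1 below-mean | 0.1140 − 0.0296 = 0.084 | 5.8% |
| 20% v 10% | only below-mean | 0.1995 − 0.0887 = 0.111 | 6.6% |
| 20% v 20% | 2:1 in opposite directions | 0.0665 + 0.0665 = 0.133 | 7.0% |
| 30% v 10% | only below-mean | 0.3420 − 0.0887 = 0.253 | 12.7% |

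Swapping the arms reverses the sign of the shift.

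**The case against.** The window has a rationale. It is stated in advance, depends on timing rather than on a score, allows a week either side of the instructed period, and standardises measurement of an effect that may wane: Aim 1c asks when symptoms return, and section 2.0 reports 9% of the investigators' own series returning to baseline. Patients are blinded, so with no true effect they have little reason to return at different times by arm. Numbers are cushioned. All of this stands, and it is why the point is conditional. It does not answer the absence of an as-randomised comparison, and spare recruitment replaces lost numbers, not selectively lost ones.

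A reader might infer three stronger things.

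- *The primary result is biased.* The documents do not support this. They contain no out-of-window rate by arm and nothing linking lateness to outcome.
- *Removal depends on outcome by design.* For patients reporting 0/10 after the first injection, "their condition would be considered cured and their enrollment in the study will finish", so they have one visit exposed to the window and the others have two. This matters only if one out-of-window visit removes the whole patient, which the text does not say, and it is small even then. Suppose 10% of visits fall outside at random and full resolution is 30% v 10% (both assumed). The analysed rates are 0.27/(0.27 + 0.567) = 32.3% and 0.09/(0.09 + 0.729) = 11.0%, a difference of 21.3 points instead of 20. With equal resolution it is zero, so type I error is not raised.
- *The daily log is lost too.* The patient log is described thus: "This will include a visual analogue scale to be completed daily after each injection to document cough severity". It does not depend on the visit day, but its loss also requires the whole-patient reading, with which the n = 25 side-effect denominators fit poorly.

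**Conclusion.** The concern holds in conditional form and should be fixed. The removal rule is explicit, acts after randomisation, reaches completed primary-outcome data, and is not balanced by any planned as-randomised between-arm LCQ analysis. Confidence in that is high; confidence that material bias would follow is not, because no document gives the rates.

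On the assumed scenarios, one-directional 2:1 selection with unequal removal does little (0.04-0.08 SD, type I error 5.2-5.8%). It takes strong selection to reach 0.11-0.13 SD (6.6-7.0%) and an extreme case to reach 0.25 SD (12.7%). An identical mechanism and rate in both arms does nothing. The direction cannot be predicted. Power is secondary: on section 6.0's own assumptions, 7 of 25 per arm could be lost before the stated 18 is reached.

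**What to change.** Replace the removal rule with:

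> All randomised patients are analysed in the arm to which they were assigned. LCQs collected at follow-up outside 1-4 weeks are kept, with the actual visit day recorded. LCQs completed after an open-label injection are not used in the randomised comparison; LCQs completed after unblinding but before any open-label injection are kept and flagged. Out-of-window visits and patients with no post-injection LCQ are reported by arm. The analysis restricted to 1-4 week visits is a sensitivity analysis.

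Post-unblinding LCQs are flagged rather than dropped because unblinding is set at 2 weeks after the second injection and follow-up is instructed at 2 to 3 weeks. Dropping them could discard many second-injection LCQs from patients who followed the instructions.

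The cost is protocol wording, recording the visit day and one extra analysis, with no added visits or patients. The downside is more spread in visit timing, and some late LCQs may reflect a waned effect, which the 1-4 week sensitivity analysis would show. Patients who never return have no follow-up LCQ under either rule. The wording does not choose a method for them; counting them by arm is the minimum.

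Separately, the sponsor must reconcile, within section 10.0, unblinding at 2 weeks after the second injection with the 2-3 week instructed and 1-4 week accepted follow-up. No schedule is proposed here.
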